#### Psychological risk

Risks for participants also include those associated with the inconvenience of participation including answering surveys, providing saliva, urine, and participating in follow-up visits and assessments. To minimize the inconveniences associated with study participation we will review all data collection instruments and study procedures to minimize the number of items in our instruments and improve the accessibility and convenience of our study procedures. We anticipate using several methods to enhance convenience to participants, including offering study visits in the evening and on weekends and offering patients a choice of where they will be seen (KUMC or Swope). Another risk is feeling pressured to be in the study, which we will track in order to monitor and will report this as an adverse event.

Social risk

None

#### Economic risk

None

#### Potential benefit of participating in the study

There are also no direct benefits to participating in this study except that researchers hope that the information from this research study may be useful in informing the FDA's regulatory action on menthol flavoring in EC.

#### G. Location where study will be performed:

The study will take place at The University of Kansas Tobacco Treatment Center at Swope, [name], in Kansas City, Missouri (hereafter referred to as Swope) or at the KUMC CRU in Fairway, Kansas based on the preference of each participant. All data will be directly entered into an electronic data capture system (i.e., RedCap or CRIS), therefore minimizing the use of paper records. If paper records are generated, they will be stored in locked file cabinets at Swope. Only study staff will have access to the locked records at Swope and the secure online electronic data capture system.

#### L. Assessment of Subject Safety and Development of a Data and Safety Monitoring Plan

The current study involves an EC that is publicly marketed and commercially available for purchase to anyone over the age of 21. ECs are a tobacco product and are being provided for non-therapeutic purposes. ECs are no more harmful than conventional cigarettes, and various studies suggest that they may offer reduced harm.

This study does not involve more than minimal risk. We will protect participants and minimize risks by using the strict exclusion criteria and careful monitoring of adverse events (AEs). AEs will be tracked during regularly scheduled visits or through spontaneous reports made by participants. [name] will be made aware of unexpected or serious AEs within 24 hours of the first report by participants; all other AEs will be reviewed weekly by [name]. SAEs will be reported to the KUMC IRB, FDA, and NIDA within 24 hours of first awareness of the event. Unexpected adverse events that are related to the study medication will be reported to KUMC IRB, FDA, and NIDA within 5 working days of first awareness of the event if the event is not serious fatal and within 24 hours of first awareness if the event is serious. Unexpected adverse events that are unrelated to the study medication will be reported to the KUMC HSC during yearly routine event reporting. IRB actions taken in this study will be reported to NIDA. [name] (or the treating provider) will determine relatedness for each reported AE. SAEs will be defined as any event experienced by a study subject while on the study medication that is fatal, life-threatening (subject was at risk of death from the event as it occurred), disabling or incapacitating, requires inpatient hospitalization or prolongs a current hospitalization, is a congenital anomaly in the offspring of a subject who received the study medication, or required intervention to prevent permanent impairment or damage.

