#### B. Study Type and Design

Menthol smokers (n=800), stratified by race and gender, who are not interested in quitting nicotine will be randomized 1:1 into a 12-week open label, non-inferiority trial comparing a 4th generation nicotine salt-based pod-system EC in menthol or tobacco flavoring. Each group will be provided a 12-week supply of EC 5% nicotine concentration in either menthol or Virginia tobacco and will complete 4 check-in sessions to facilitate switching to EC. The primary outcome is the proportion who make a complete or predominant switch to EC at week 12, where complete switching is defined as exclusive use of EC, biochemically confirmed with CO < 6, and predominant switching is defined as use of EC with > 50% reduction in CPD. Secondary outcomes include acceptability and long-term effectiveness. Follow-up will continue through week 26 to examine long-term maintenance of EC product use and smoking behavior under naturalistic conditions. Participants will be recruited and enrolled in collaboration with The University of Kansas Health System and Swope Health Central (Swope), a federally qualified health center serving a predominately AA population, that has been the site for our previous trials.

**Why a non-inferiority trial?** Non-inferiority trials are executed when one product is anticipated to be 'not unacceptably worse than' a comparator product and have value when it is feasible to sacrifice some degree of benefit to gain advantages provided by another product.  In the case of EC flavoring, the tradeoff of lower efficacy and acceptability of tobacco EC to adult menthol smokers may be well worth the advantages gained in youth and young adult initiation so long as the difference between tobacco and

menthol EC is not so large that adult menthol smokers are unwilling to use tobacco EC. The alternative would be a superiority study, but these are used to conclude that one product is better than the other, and at the time of this proposal there is no data supporting this approach that menthol EC are more effective than tobacco EC at facilitating a switch from tobacco cigarettes to EC or vice versa. Rather, data from our RCT and other studies suggest that tobacco EC are non-inferior to menthol EC in terms of effectiveness and acceptability to adult users, but a fully powered RCT is needed.

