**Aim 4. Examine the long-term effectiveness of menthol versus tobacco EC at week 26.** We will compare switching patterns at week 26 to examine long-term maintenance of EC and smoking patterns under naturalistic conditions (EC only provided up to week 12). **Hypothesis 4.** *There will be no statistically significant difference in rates of complete or predominant switching at week 26 between those randomized to menthol versus tobacco EC.* For this aim we will calculate the proportion of complete and predominant switchers as defined above but at week 26. We will then calculate the corresponding 95% confidence interval on the difference in these proportions. The lost to follow-up rate at month 6 in the RCT that forms the basis for this proposal was < 10%. We do not expect the lost to follow-up rate to exceed 20% at month 6; however, given that we are not sure of our loss to follow-up rate we will report complete and

predominant switching at month 6 assuming those lost are not complete or predominant switchers and subsequently report on completers only.

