#### **OTHER CONSTRUCTS OF INTEREST**

#### Safety and tolerability

• *Side Effects.* A symptoms checklist will be used to assess participants experience (yes/no) of common smoking/vaping related side effects, including cough, dry mouth, shortness of breath, mouth and throat irritation, headache, dizziness, nausea or vomiting, and increased heart rate/palpitations. For each side effect reported, participants will be asked whether they attribute the side effect to cigarettes, EC, or both.

• *Safety.* Adverse events observed or reported will be recorded at each in-person visit. Assessments as to seriousness, severity, and the relationship to treatment and other causes will be made. Serious adverse events will also be captured in the centralized database. AEs and SAEs will be reported to the appropriate regulatory agencies.

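### The SAE definition stops when a participant is no longer on study product, so serious events in the 14 weeks after supply ends lose the SAE label and the unconditional 24-hour report

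*Combined protocol and SAP*

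**What the plan says.** Section II.L (Assessment of Subject Safety) gives the only definition of an SAE in the text: "SAEs will be defined as any event experienced by a study subject while on the study medication that is fatal, life-threatening", followed by the other usual seriousness criteria. The term study medication is not defined. The same section sets three reporting rules:

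- For SAEs: "SAEs will be reported to the KUMC IRB, FDA, and NIDA within 24 hours of first awareness of the event".
- For unexpected events related to the study medication: five working days, or "within 24 hours of first awareness if the event is serious".
- For unexpected events judged unrelated: "Unexpected adverse events that are unrelated to the study medication will be reported to the KUMC HSC during yearly routine event reporting".

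On timing, section II.B says "Follow-up will continue through week 26 to examine long-term maintenance of EC product use and smoking behavior under naturalistic conditions". Aim 4 in section II.C describes the week-26 comparison as "under naturalistic conditions (EC only provided up to week 12". Section V.B (Safety and tolerability) says "Adverse events observed or reported will be recorded at each in-person visit", with seriousness, severity and relationship assessed. It also says that AEs and SAEs go to the appropriate agencies, but sets no time limit. The schedule shows visits with breath CO at weeks 18 and 26, so both are in person.

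**The concern.** The condition attached to the SAE definition is narrower than the period over which the trial observes people. Product supply ends before the midpoint of follow-up, and no section reviewed adds a post-supply window. The trial encourages participants to take up EC and then deliberately watches whether they keep using it unsupplied, so the later weeks include exposure that the trial set in motion.

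What is at stake is classification and prompt external notice. Section IV.E says that no ongoing third-party monitoring is planned, so the written definition is one of the main safeguards. Two teams following the same text could also label the same week-16 admission differently, which would make the final SAE table hard to interpret.

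**Working it through.** **1. Which rule applies to a serious event.** Setting the section II.L rules side by side:

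| Type of serious event | While on study product | After supply ends, plain reading |
|---|---|---|
| Unexpected and related | SAE, 24 hours | 24 hours if serious has its ordinary meaning; five working days if it carries the SAE condition |
| Unexpected and unrelated | SAE, 24 hours | Yearly report |
| Expected | SAE, 24 hours | No route with a time limit |

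Two examples at week 16. A death judged unexpected and unrelated would go into the yearly report. An admission for breathlessness could be judged expected, because section II.F lists that symptom among the common EC side effects; it would then have no timed external route.

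**2. How much follow-up is uncovered.** Inputs: 800 participants and follow-up to week 26 (II.B); supply to week 12 (I.A, II.C Aim 4, and II.E, which describes 4-week supplies at weeks 0, 4 and 8).

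- Weeks: 26 − 12 = 14; 14/26 = 53.8%.
- Person-weeks: 800 × 14 = 11,200 of 800 × 26 = 20,800.
- Person-years: 11,200/52 = about 215.

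The schedule table and one heading under Procedures and Methods list week 12 for EC, against the text beneath that heading and the EC paragraph under Treatment Overview. These places must be reconciled, because they determine when product use under the trial ends. If the mark meant a further 4-week supply, the uncovered part would be 26 − 16 = 10 weeks, 10/26 = 38.5%, or 8,000 person-weeks.

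**3. How many events.** The documents give no SAE rate. I assume 2 to 15 per 100 person-years.

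- No loss to follow-up: 215 × 0.02 = 4.3; 215 × 0.15 = 32.3. About 4 to 32.
- With 20% loss (the ceiling Aim 4 allows at month 6): 215 × 0.80 = 172; 172 × 0.02 = 3.4; 172 × 0.15 = 25.8. About 3 to 26.

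These count all serious events in weeks 12–26. The documents do not allow the unexpected and related ones, which have their own route, to be subtracted.

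**4. Before week 12.** Section V.B provides for participants who use no EC, and section II.D expects no terminations by the investigator, so people off product stay in the study. Whether they are still on study medication depends on a term that is not defined.

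**The case against.** The strongest reply is that nothing is lost. AEs are tracked at scheduled visits and through spontaneous reports with no stop at week 12, seriousness is assessed, and section II.L requires internal notice of serious AEs within 24 hours. That stands. A reader might infer that serious events go unrecorded for more than half of follow-up; the documents do not support this. The gap lies in the SAE label and in expedited external reporting.

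Second, unexpected related events have a 24-hour route with no explicit on-product condition. That also stands, and it narrows the gap to events that are expected or unrelated. It leaves some doubt over the rest, because serious is not defined anywhere else.

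Third, being on study medication could mean the 12-week supply phase and not current vaping. On that reading a participant who stops at week 3 and is admitted at week 5 is covered, so the point about early stopping is arguable only. Conversely, someone using leftover or self-bought EC after week 12 might be argued to be still on product. Both readings rest on a term the plan leaves open.

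A reader might also infer a safety bias between arms, with the flavour abandoned sooner looking safer. The plan's 0.73 and 0.64 cannot be used to size this. Non-switchers include partial switchers, who still vape, and people lost to follow-up who are counted as failures. The 0.64 is the non-inferiority bound, and the plan's 82% power is reproduced at 81.8% with 0.73 in both arms. No between-arm SAE test is planned either.

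Finally, a reader might think the congenital-anomaly criterion cannot be met. It is worded "is a congenital anomaly in the offspring of a subject who received the study medication", which sets its own condition of past receipt, so the argument is weak.

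**Conclusion.** The point holds as a defect in a stated rule. As written, serious events after supply ends that are expected or unrelated are not SAEs and have no expedited external report; the unexpected unrelated ones reach only the yearly report. The affected period is 14 of 26 weeks (54%), or 10 of 26 (38%) under the alternative reading of the dispensing schedule. The count of 4 to 32 events, or 3 to 26 with 20% loss, is an upper range resting entirely on an assumed rate. The conclusion does not need it. Extension to participants who stop EC before week 12 is possible but depends on an undefined term. Efficacy analyses, sample size and power are unaffected. The text between sections II.G and II.L was not available for this check; an SAE window stated there would settle the matter.

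**What to change.** In section II.L, replace the on-medication condition in the SAE definition with a fixed window: from first dispensing (week 0) through the week-26 visit, for every randomised participant, whether or not EC is being used. Then:

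- Make Safety and tolerability in section V.B refer to that same definition and window.
- Add one field to the SAE form for the product in use at onset (study EC, other EC, cigarettes).
- Report SAEs by randomised arm, separately for weeks 0–12 and weeks 12–26.
- Reconcile the conflicting statements on week-12 dispensing, so that the boundary between the two reporting periods is clear.

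No new visits are needed, because AEs are already recorded at weeks 18 and 26. The cost is one protocol sentence, a cross-reference and one form field. The downside is a few more expedited reports, most of them probably judged unrelated.

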#### **B.** Screening Interview/questionnaire

The screening interview will take place over the phone or in person and be conducted by a member of the study team. The screening questionnaire will address the general inclusion/exclusion criteria in the Eligibility Criteria table above. Only participants who have expressed interest will be screened.

#### C. Informed consent process and timing of obtaining of consent

Consent will be obtained prior to participant involvement. Individuals interested in the proposed study will meet the research assistant at Swope or the CRU. Each individual will be given a copy of the consent form and as much time as they need to review its contents. After the consent form is read, both the individual and the research assistant will review the consent form together and the potential participant will be encouraged to ask questions. Each individual will be reminded that participation in the study is completely voluntary and their decision to participate will not affect their current or future medical care at the treating facility. The consenting process will take place in a private location.

#### D. Alternatives to Participation

Alternatives to participating in the study are continue to smoke cigarettes as usual or switch to other alternative sources of nicotine, including purchasing nicotine gum or patches from the pharmacy or obtaining a prescription for nicotine inhaler, nicotine nasal spray, or nicotine lozenge.

#### E. Costs to Subjects

There are no costs to subjects. All tests, procedures, and visits are being performed solely for research purposes and are not billable to insurance companies.

# F. How new information will be conveyed to the study subject and how it will be documented

We have plans to publish data from this study in aggregate but will not provide any individualized feedback to participants.

#### G. Payment, including a prorated plan for payment

Participants will be given a \$40 electronically loaded ClinCard at Wks 0, 4, 8, 12,18, and 26 as compensation for their time/travel. To encourage use of the study provided EC, an additional \$20 will be provided at weeks 4, 8, 12 visits for returning EC pods, regardless of the flavor returned. Participants must complete the visit to receive the reimbursement associated with that time point. Participants may receive \$20 for each referral who is eligible and enrolls in the study. Participants may complete up to 3 different referrals for the study for a total of \$60. Travel costs will not be reimbursed.

#### H. Payment for a research-related injury

N/A

#### IV. Data Collection and Protection

#### A. Data Management and Security

Confidentiality will be maintained by assigning each participant a study identification number and numerically coding all data. The association of the ID-code and the participant's name will be kept by [name] in a locked file cabinet. The screening questionnaire and all survey data will be directly entered into RedCap or CRIS and accessible only by study staff. Any paper copies of records will be kept in a locked filing cabinet in offices that are kept locked when unoccupied. Only summaries of group data will be reported in any publications or presentations, with no identification of individuals. Because identifiable information will be collected, participant privacy will be maintained throughout the duration of the study by adhering to the regulations set forth by the HIPAA Privacy Rule. More specifically, identifiable information will not be released without written authorization of the participant. Mobile devices will not be used for data collection or storage. Identifiable data will not be sent outside of KUMC.

#### **B. Sample / Specimen Collection**

No more than 20 ml of urine and saliva will be collected at Weeks 0, 12 and 26. Samples will be stored at the Bioanalytical Laboratory at the Fairway Clinical Research Center under the direction of [name]. Samples will be accessible only to members the study team. Results from analyses will be de-identified and shared only with members of the research team. Any resulting publications will present the data in aggregate; individual participants will not be identified. For participants who agree to future testing, samples will be stored indefinitely.

#### C. Tissue Banking Considerations

For participants who agree to future testing, samples will be stored indefinitely. New biomarkers of tobacco-related harm and exposure and genetic differences in nicotine metabolism are being discovered and the stored biological samples would be used for analysis of these new markers. All samples stored for future biomarker analyses will be de-identified and accessible only to members of the study team. Results from these analyses will be de-identified and shared only with members of the research team. Any resulting publications will present the data in aggregate; individual participants will not be identified.

#### D. Procedures to protect subject confidentiality

Confidentiality will be maintained by assigning each participant a study identification number and numerically coding all data. All biological samples and survey data will be labeled with the study identification number and never with the participants name or other identifiable information. The association of the ID-code and the participant's name will be kept by [name] in a locked file cabinet and will only be accessible to members of the study team.

#### E. Quality Assurance / Monitoring

All data will be directly entered into our electronic data capture system (i.e., RedCap or CRIS) that contains edit checks to control the quality and completeness of data entry. Completeness of data entry will be automatically verified before each assessment is completed. The electronic data capture system is behind the KUMC secure firewall with role-based access that is HIPAA and human subjects compliant. There are no plans for ongoing third-party monitoring.

## V. Data Analysis and Reporting

A. Statistical and Data Analysis

#### **B. Outcome**

#### EFFECTIVENESS (Aims 1 & 4).

Switching (Primary Outcome). The primary outcome is the proportion of menthol smokers who make a complete or predominant switch to EC, defined as use of EC along with a > 50% reduction in cigarettes from baseline to week 12. The 7-day Timeline Follow Back Interview (TLFB) will be used to assess participants cigarette and EC use patterns each day for the past 7 days at each visit (weeks 0, 4, 8, 12, 18, 26). The primary endpoint is, however, fixed at week 12. The TLFB is a reliable and valid way of collecting information about substance use quantity and frequency and, in tobacco research, has been corroborated against interactive voice response, butt counts (storing and returning the butts of cigarettes smoked), and biological measures for cigarettes smoked and puff topography for EC, supporting the strong validity of this self-report measure compared to other 'gold standard' measures. For each of the last 7 days participants will be asked to recall the number of cigarettes smoked and EC sessions vaped; following standard practice, an EC session is defined as at least 15 puffs or lasting around 10 minutes. For each EC session, participants will be asked to specify the device used (i.e., study provided versus something else) and the flavor (i.e., menthol, Virginia tobacco, something else).\* For non-study provided EC, detailed information will be collected about the type of EC (e.g., brand, podbased, disposable, refillable), flavor, nicotine concentration and, if available, whether the product is nicotine salt-based. To aid in recall and corroborate self-report, participants will be given dated bags to collect all EC. Bags will be returned at each visit during the intervention phase and used to confirm use of study provided EC (i.e., grams of e-liquid consumed) and protocol adherence (i.e., the number of pods vaped in the study provided versus non-study provided flavor). *Complete switching* is defined as any use of EC and no use of cigarettes in the past 7 days (i.e., 100% reduction in CPD from baseline), biochemically confirmed with an expired breath CO < 6 parts per million (ppm). CO is used for verification because cigarettes produce carbon monoxide as a byproduct of combustion, while heating an e-liquid does not generate CO. The < 6 ppm CO cutoff is more conservative than the  $\leq$  10 ppm cutoff that is commonly used and reflects the current state of knowledge for detecting recent cigarette smoking. Predominant switching is defined as those who report any use of EC along with a > 50%reduction from baseline in CPD. A > 50% reduction has been selected because it is a measure of acceptability of the EC products and is associated with substantial reductions in biomarkers of harm and exposure relative to continued smoking and is a common endpoint used in tobacco harm reduction studies. Partial switching will be defined as those who report any use of EC along with a  $\leq$  50% reduction from baseline in CPD. No switching (i.e., exclusive cigarette user) will be defined as those who reported no use of ECs and any use of cigarettes in the past 7 days. A potential fourth group, no use of e-cigarettes or combustible cigarettes, may occur. For all switching trajectories, use of EC will be corroborated with pod counts and objectively measured EC pod weights during the intervention phase.

Other outcomes of interest include tobacco harm reduction and EC acceptability. These constructs may be measured by the following:

**TOBACCO HARM REDUCTION** (Aim 2). Tobacco harm reduction is a global topic of interest among those transitioning from cigarettes to EC and is largely driven by reduction in CPD. We expect comparable rates of switching between groups and, therefore, comparable rates of tobacco harm reduction, defined as change in each of the following constructs from baseline to week 12.

• Tobacco Quality of Life Impact Tool ( $TQOLIT^{TM}v1$ ) will be used to assess was used to assess the impact of smoking/vaping on health-related quality of life.

- *Carbon Monoxide.* Carbon monoxide will be measured in parts per million (PPM) using a coVita Bedfont Micro+ Smokerlyzer at each study visit.
- *Blood Pressure.* Systolic and diastolic blood pressure will be measures with an Welch-Allyn blood pressure cuff.
- *Respiratory symptoms* have emerged as a primary concern among EC users and, therefore, we will carefully monitor respiratory symptoms over time using the following standardized measures:

• Lung function will be assessed via spirometry. We will summarize all values returned from the spirometer (i.e., FVC, FEV1, FEV1/FVC%, PEF) but will focus our attention on *FEF 25-75%*, the pulmonary function test of small airway disease that is most sensitive to effects of cigarette smoking.

 American Thoracic Society Questionnaire (ATSQ) will be used to assess common respiratory symptoms (e.g., cough first thing in the morning, wheezing, shortness of breath, etc.). This measure was selected because it contains items relevant to acute respiratory effects experienced by some cigarette smokers when they initiate EC.

• Leicester Cough Questionnaire (LCQ) is a valid, repeatable measure of chronic cough which is responsive to change, especially the onset of cough in established cigarette smokers when they initiate EC.

It is not within the scope or budget of this study to examine additional biomarkers of exposure or potential harm, but we will collect urine and saliva samples from all participants at weeks 0 and 12 and bank them for future analyses. Potential biomarkers of interest have been selected to align with other studies and because they represent categories of toxicants commonly found in tobacco products and tobacco smoke that have been classified by the FDA as contributing to respiratory, cardiovascular, and cancer-related diseases associated with smoking.

